4.6 Subject Replacement

Subjects who are enrolled initially and then found not to meet inclusion criterion will be replaced in order to provide 20 patients eligible for randomization and trial completion.

5. Study materials

5.1 Study drug reconstitution and administration

Panhematin[™] (human hemin), a lyophilized preparation of hematin (hydroxyheme or heme hydroxide), is provided by Recordati Rare Diseases in a vial containing either 350 mg of product, and reconstituted with 147 mL of 25% human serum albumin ^{43,50}. Standard directions for dose preparation using either vial are in place in the UTMB Pharmacy and are reflected here.

The patient's body weight is provided to the Pharmacy, which prepares each Panhematin[™] dose of 4 mg/kg body weight. Representative calculated dosages are shown in the **Table**. No more than 313 mg should be used for each administration, i.e. the dose is 4 mg/kg body weight, not to exceed a total of 313 mg. After the first dose, the same calculated dosage is used for subsequent doses.

The dose should be calculated and venous access obtained before reconstituting the study drug.

Procedure for reconstitution of Panhematin^{™ 50}.

The following materials are needed:

1. One 350-mg vial of Panhematin™.		of heme-albumin sed on representa	
2. One 150-mL or	weights		
larger sterile empty	Body Weight	Hemin dosage	Heme–Albumin
glass bottle for	(kg)	(4 mg/kg)	Mixture (mL)
infusion; a second	50	200	83
bottle is needed for	60	240	100
processing the	70	280	117
350-mg vial of	80	313*	132
Panhematin.	* No more than 3	313 mg Panhematii	n™ should be
3. Three 50-mL vials	used per single of	lose.	

- of 25% albumin (only 147 mL will be used)
- 4. One 5-micron filter needle
- 5. One vent needle.

To prepare Panhematin[™] for infusion. (Note that the 350-mg vial requires 147 mL of 25% albumin. Because only 132 mL of 25% albumin will fit in the vial, this amount is used initially, followed by the additional 15 ml of 25% albumin):

- Reconstitute the 350-mg vial of Panhematin[™] initially with 132 mL of 25% albumin. Because this volume will almost completely fill the vial, the albumin must be injected into the vial slowly and the vial must be vented. Use a vented needle or make a vent with a separate needle to release the air pressure.
- 2. Do not shake the mixture. Swirl the vial 15 to 20 times to ensure that it is thoroughly mixed (it will be difficult to see if the materials are blended because of the dark color of hemin).
- 3. Withdraw the full contents of the vial into a syringe.
- 4. Inject the full contents (350 mg hemin reconstituted with 132 mL 25% albumin) into a 150-mL empty sterile bottle.
- After the full contents is transferred to a sterile glass bottle (as described in step 4 above) add an additional 15 mL of 25% albumin to the original vial, swirl as in step 2 and transfer this using a syringe to the same 150-mL bottle, which will now contain 350 mg hemin reconstituted with 147 mL of 25% albumin.
- 6. After reconstitution of the entire contents of the vial (350 mg hemin) with 147 mL of 25% albumin, the concentration of hemin in the glass bottle is 2.4 mg/mL. The volume required to deliver the desired dose (usually 4 mg/kg of body weight) should be calculated based on the patient's body weight, but not to exceed 313 mg. See **Table** for example volumes for some example body weights.
- 7. Withdraw the calculated required dose for the patient into a syringe by using a 5-micron filter needle.
- 8. Inject the dose into a 150-mL empty sterile bottle.
- 9. Label the bottle.
- 10. Place the bottle in an amber bag to protect the mixture from light. Also place a vented spike adapter in the bag. To preserve blinding, do not label the amber bag. (Customarily, a yellow Medication Administrations Recording blood products label (for both albumin and Panhematin[™]) would be attached to the amber bag.) Then place the amber bag inside a STAT-labeled bag.
- 11. Hand-deliver the bag to the clinical unit immediately. The infusion should be started within 1 hour or less of preparation. The infusion is administered by an unblinded nurse and other blinding procedures are followed (as described in sections **5.2 and 5.5**). The heme–albumin complexes may be

stable for much longer, but the solution does not contain bacteriostatic agents and therefore should be infused promptly.

Procedure for administration of Panhematin™.

- 1. Access a large peripheral vein using an indwelling intravenous catheter. Based on clinical indications, such as a need for frequent intravenous infusions or poor venous access, a peripherally inserted central line or a central line or port may be used.
- 2. Piggyback the Panhematin[™]-albumin dose to an intravenous line that is infusing 0.9% sodium chloride at a moderate rate (at least 100 mL/hr). The piggyback site should be as close as possible to the venous access site.
- 3. Infuse the dose over a period of 60-90 minutes or at a rate that should not exceed 1 mL/min, which corresponds to the recommendation for infusing 25% human albumin ^{43,50}. A somewhat shorter infusion time may be acceptable but may entail some risks from intravascular volume expansion. Some patients have experienced headaches shortly after infusions of heme–albumin, perhaps related to transient expansion of intravascular volume.
- 4. After the heme–albumin is infused, continue the infusion of 0.9% saline for at least 10 minutes at a rate of at least 100 mL/hr to clear the line, catheter (or port) and vein of the drug.

The study drug is administered at a dose of 4 mg/kg body weight. The infusion is given over 60-90 minutes ⁵⁰, after which the IV set and other materials are removed and discarded.

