3.3 Treatment of Subjects and Rationale for Treatment

Panhematin TM 4 mg/kg will be reconstituted with 25% human albumin ⁵⁰ and infused over a 1 hour period. The amount of albumin is based on achieving a 1:1 molecular ratio for hemin and albumin 43,50 . Product labeling suggests that

Panhematin[™], after reconstitution with sterile water, be infused within 15 minutes. After reconstitution with albumin, an infusion time of 1 hour is based on guidelines for infusion of the amount of human albumin used for reconstitution. The longer infusion time of 1 hour is acceptable given the enhanced stability of hemin in the presence of albumin, and based on experience of investigators in the Porphyrias Consortium ⁹.

Glucose infusions will be permitted during the study for treatment of acute attacks. Its use will be recorded but will not be specified by the study. For treatment of acute attacks, Panhematin[™] product labeling suggests an initial trial of glucose at a dose of 400 grams daily, whereas a dose of 300 grams daily as 10% glucose is generally accepted ^{9,68-70} and a higher dose given as 10% glucose may increase the risk of fluid overload and hyponatremia. Smaller amounts (e.g. 200 grams as 2L 5% glucose in saline) have been recommended for meeting fluid, electrolyte and caloric needs, but not as an alternative to hemin therapy ⁷¹. There are no guidelines or published experience for glucose loading for prevention of attacks, but based on expert experience the impression is that it is not very effective and may lead to unwanted weight gain.

Symptomatic treatment, including opioids, needed to control pain and other symptoms during an attack that occurs during the study will be recorded. Use of medications needed to control chronic symptoms, including pain, will also be recorded.

4. Trial Population

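### Section 5.1 gives an infusion time and a maximum rate that agree only up to about 54 kg: a minor inconsistency in the administration rule

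*Combined protocol and SAP*

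**What the plan says.** The infusion speed of the study drug is described in four places.

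- Section 5.1, administration step 3: "Infuse the dose over a period of 60-90 minutes or at a rate that should not exceed 1 mL/min". The clause that follows the rate gives its basis: "which corresponds to the recommendation for infusing 25% human albumin". The next sentence allows some latitude and attaches a caution: "A somewhat shorter infusion time may be acceptable but may entail some risks from intravascular volume expansion".
- Section 5.1, closing paragraph, with no rate: "The infusion is given over 60-90 minutes".
- Section 3.3, with a single time and an albumin rationale: "an infusion time of 1 hour is based on guidelines for infusion of the amount of human albumin used for reconstitution".
- Section 5.2, which calls the infusion a one-hour infusion when it describes removal of the IV set, and has placebo (117 mL of saline) given in the same manner as active drug.

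The volumes come from the dose table and reconstitution text in 5.1. On dose, "the dose is 4 mg/kg body weight, not to exceed a total of 313 mg". On strength, "the concentration of hemin in the glass bottle is 2.4 mg/mL". The table lists 83, 100, 117 and 132 mL for 50, 60, 70 and 80 kg.

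**The concern.** Step 3 sets a time and a rate side by side. The rate is linked to albumin guidance there, and one hour is linked to albumin guidance in 3.3. A reader would expect the figures to describe roughly the same infusion. For most tabulated weights they do not, so staff following different sentences of the same protocol would give the same patient quite different infusions.

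What is at stake is administration and, modestly, safety. The protocol itself connects shorter infusion with intravascular volume expansion and, tentatively, with headache. Section 13.1 notes that albumin could worsen heart failure, significant chronic anemia or advanced kidney disease, and does not exclude patients with these conditions. Tolerability of albumin reconstitution is also something the trial wants to describe, and that is easier to interpret when the speed is standardised.

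**Working it through.** **Inputs, all from section 5.1:** dose 4 mg/kg, capped at 313 mg; concentration 2.4 mg/mL (350 mg in 147 mL is 2.381 mg/mL); table volumes 83, 100, 117 and 132 mL; time 60-90 minutes; rate at most 1 mL/min. Section 3.3 adds one hour.

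**Step 1: reproduce the table volumes.** Volume = dose / concentration.

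- At 2.4 mg/mL: 200/2.4 = 83.3; 240/2.4 = 100.0; 280/2.4 = 116.7; 313/2.4 = 130.4 mL.
- At 350/147 mg/mL: 84.0, 100.8, 117.6 and 131.5 mL.

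All are within 2 mL of the table, so the table is sound and was read correctly.

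**Step 2: rate implied by each time, and time implied by the rate.** Rate = volume / minutes. Minimum time at 1 mL/min = volume in mL / 1, so minutes equal millilitres.

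| Weight | Volume | Rate over 60 min | Rate over 90 min | Minimum time at 1 mL/min | Times meeting both |
|---|---|---|---|---|---|
| 50 kg | 83 mL | 1.38 mL/min | 0.92 mL/min | 83 min | 83-90 min |
| 60 kg | 100 mL | 1.67 mL/min | 1.11 mL/min | 100 min | none |
| 70 kg | 117 mL | 1.95 mL/min | 1.30 mL/min | 117 min | none |
| 80 kg | 132 mL | 2.20 mL/min | 1.47 mL/min | 132 min | none |

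One hour is above 1 mL/min in 4 of 4 rows, and 90 minutes is above it in 3 of 4.

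**Step 3: weight at which the two part.** Volume per kg = 4/2.4 = 1.667 mL/kg. The rate can be held within 60 minutes up to 60/1.667 = 36 kg, and within 90 minutes up to 90/1.667 = 54 kg. The dose cap applies from 313/4 = 78 kg, so the 80 kg row also stands for every heavier patient.

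**Step 4: size of the gap.** Minimum time at 1 mL/min less 90 minutes: 10, 27 and 42 minutes at 60, 70 and 80 kg. Less 60 minutes: 23, 40, 57 and 72 minutes at 50, 60, 70 and 80 kg.

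**The case against.** The strongest reply is that no instruction is contradicted as written. Step 3 says *or*, so testing both conditions together asks for something the text does not require. The rate is worded with *should*, and the next sentence tolerates a somewhat shorter time. The clause about albumin follows the rate and need not cover the time. The text also leans toward time as the working rule: 5.1 gives 60-90 minutes twice, 3.3 and 5.2 give one hour, which lies inside that range, and the rate appears once.

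Most of this stands. A nurse complies by either route, and 1 mL/min reads as guidance. It does not make the figures agree. Section 3.3 rests one hour on albumin guidelines, step 3 rests 1 mL/min on the albumin recommendation, and at these volumes both cannot describe the same guidance. From 60 kg upward, a nurse who takes the rate route runs past the 90 minutes in the closing paragraph of 5.1. The latitude for a somewhat shorter time hardly covers the gap at 80 kg, where 60 minutes is less than half of 132.

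A reader might go further and infer that patients are exposed to an unsafe rate. The documents do not show this. Nothing in them establishes that 1.38 to 2.20 mL/min is harmful, the volume is capped at 132 mL, the unblinded nurse stays throughout, patients at risk are to be observed closely, and 13.1 expects little or no added risk over usual prophylaxis. A reader might also infer that infusion length reveals the arm. That is not supported either: placebo is given in the same manner, the patient is blindfolded, and blinded staff are out of the room.

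**Conclusion.** A minor but real internal inconsistency in a drug-administration rule. At the tabulated volumes, one hour runs at 1.38 to 2.20 mL/min and 90 minutes at 0.92 to 1.47 mL/min, and a duration that satisfies both the time range and the rate exists only up to about 54 kg. At 80 kg and above the gap is 42 minutes from the upper end of the time range and 72 from one hour.

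The arithmetic rests only on the protocol's table and stated concentration. Efficacy analysis, alpha and power are unaffected. The documents do not settle which figure matches the cited albumin guidance. The text favours time as the working instruction, but frequency of mention does not show that the rate is the mistake.

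**What to change.** State one instruction and use it in 3.3, in both places in 5.1 (step 3 and the closing paragraph) and in 5.2.

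**Default.** Keep the protocol's own 1 mL/min as the ceiling, since it is the slower of the two routes from 60 kg upward and the protocol's stated worry is faster infusion. Replace the one-hour and 60-90 minute wording. Add a column of minimum durations to the dose table: 83, 100, 117 and 132 minutes. For other weights the minimum in minutes equals the prepared volume in mL. Run the 117 mL placebo for the same weight-based duration, so that the arms stay matched in length once the time depends on weight.

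**Alternative.** If the site checks its source and 60-90 minutes proves to be the intended limit, delete the 1 mL/min figure and make 3.3 and 5.2 read 60-90 minutes. Do not replace it with a rate back-calculated from volume and time.

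**Cost.** The alternative changes text only. The default lengthens infusions by up to 42 minutes beyond 90, or 72 beyond one hour. The pharmacy should confirm that this is acceptable, because "the solution does not contain bacteriostatic agents and therefore should be infused promptly". Slower infusion may also add carrier saline. Assuming the line runs alongside the dose at the stated minimum of 100 mL/hr (the text does not say that it does), the 80 kg row would carry 100 × 132/60 = 220 mL, against 100 mL in 60 minutes and 150 mL in 90. The clinical team should weigh this, since volume is the reason for slowing the infusion.

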5.2 Placebo preparation and administration

It is not feasible to design a placebo for intravenous administration with the same appearance as Panhematin[™] (human hemin), which is administered as a black solution. The placebo for this study will be 117 mL of 0.9% sterile saline in the same 150 mL sterile glass bottle used for the active drug, and labeled and delivered from the Pharmacy in the same manner as the active drug. The placebo will be infused in the same manner as the active drug by a research nurse who is unblinded. Other study personnel will remain blinded. To maintain blinding in this study, study drug (reconstituted Panhematin[™] or placebo) is delivered from the Pharmacy in a non-transparent container, so is not visible to study personnel or the patient. One research nurse will have responsibility for the infusion and will not be blinded. This nurse will interact minimally with the patient and other study personnel and will drape the administration set and the IV site in a manner that will maintain blinding. The drug or placebo will be administered through an already established intravenous access. The unblinded nurse will remain for the entire infusion time and assist in any manner necessary to maintain blinding of other study personnel and the patient, which may include adjusting drapes and the infusion set-up. The unblinded nurse will not otherwise be involved in the patient's care or in collecting data. At completion of the one-hour infusion, the unblinded

Porphyria Laboratory and Center Date: June 18, 2019 IND 13,929

nurse will remove the IV set and other materials to another location for disposal. The patient will also be blind-folded before the study drug arrives and until the IV set and other materials are removed from the unit. Other research nurses who are blinded will carry out other study procedures that do not involve the infusion.

5.3 Timing of administration of Panhematin[™] or placebo

Treatment with Panhematin[™] or placebo should be given within ±2 days of the time a prophylactic dose or series of doses would have been administered. Panhematin[™] is FDA approved at the dosage level used in this study.

It is recommended in product labelling that Panhematin[™] be given once or twice daily. Therefore, in this study a dose of Panhematin[™] will not be given within 12 hours of a previous preventive dose of active study drug. If an attack occurs within 12 hours of the study dose of Panhematin[™] or placebo, open label treatment with Panhematin[™] will be delayed until 12 hours after the last study dose of Panhematin[™] or placebo. If it considered clinically necessary to start open label Panhematin[™] for treatment of the attack in less than 12 hours, the first therapeutic dose for the attack will be blinded, and will be Panhematin[™] if the patient was randomized to placebo, and will be placebo if the patient was randomized to Panhematin[™]. Whether active drug or placebo is given in this instance will be determined by the Pharmacy, where 1-2 individuals will not be blinded.

5.4 Glucose administration

Glucose loading will be permitted for treatment of acute attacks during the study at the discretion of the patient's physician. No particular amount or regimen will be required during participation in this study, although a recommendation may be made to treat intravenously with glucose 300 grams daily, which is considered the standard dosage for glucose loading ^{9,10,68-70,72}. This amount is usually delivered as 3 liters of 10% glucose infused daily for 4 days or longer. Although larger daily amounts are sometimes recommended, this results in larger volumes of intravenous fluid and increased risk for fluid overload and hyponatremia.

5.5 Blinding

Blinding of treatment with a darkly colored, intravenous drug poses significant challenges, but is feasible because the drug is administered only once, and personnel directly involved in drug reconstitution and administration will be different from those who establish intravenous access and are otherwise involved in the study patient's care. The PI, other physicians, study coordinators and nurses involved in patient care will remain blinded. As described above (Section 5.2), pharmacy personnel (1-2 individuals) and one study nurse who will administer the drug will not be blinded. Blinded staff will not be in the room during study drug administration. Every effort will be made to avoid compromise in blinding if, for example, there are problems with the infusion after it is started. Problems with the infusion will be handled by the unblinded nurse without compromising blinding of other personnel, if possible. Any difficulties that might compromise blinding will be recorded.

Porphyria Laboratory and Center Date: June 18, 2019 IND 13,929

5.6 Treatment of acute attacks during the study

Attacks during the study that occur at the study site will be treated at the study site with the usual hemin regimen of 4 mg/kg body weight daily for 4 days, or longer if clinically indicated, as part of the study. Attacks that occur after the patient leaves the study site and returns home will be treated in the manner considered optimal by the patient's physicians. Such treatment will be recorded but not prescribed by the protocol. Study site physicians will be available to provide advice on management, as appropriate. This will not be considered formally as rescue treatment since it is not prescribed in the study protocol. It will be recommended that Panhematin[™] be reconstitution with human albumin, as described above, since this is now considered optimal ⁹. Blinding of the study treatment will be maintained during unblinded treatment of any acute attacks, unless doing so would compromise patient safety.

Administration of two Panhematin[™] doses of 4/mg/kg doses daily was common in the past, although a single daily dose for 4 days is now more commonly recommended ⁹. When two doses are given, an interval of at least 6-8 hours is customary. During this study, a need to give two doses of Panhematin[™] within a period of 12 hours will occur only if an acute attack develops and needs to be treated within 12 hours of the previous study dose of Panhematin[™] or placebo.

As noted above, if open label treatment with Panhematin[™] is required less than 12 hours after a blinded infusion, the first infusion for treating the acute attack will also be blinded, and the first infusion will be Panhematin[™] if the patient was randomized to placebo, and will be placebo if the patient was randomized to Panhematin[™]. This will avoid unblinding of the randomly assigned study treatment.

Symptomatic treatment for pain, nausea and vomiting will be given as needed to control these symptoms of the porphyric attack, which can be severe. These are regarded as expected treatments rather than rescue treatments and are not a prescribed part of this study.

5.7 Randomization

Treatment in this double-blind, symmetrically randomized, parallel group trial study will be assigned by the study statistician, who will inform the Pharmacy of the assignment. Randomization will be in blocks of 4, and occur after the inclusion and exclusion criteria are satisfied. Labels showing the study randomization number will be generated to label all study samples and materials.

The randomization code for a particular subject can be broken if knowing the identity of the treatment allocation is felt to be necessary for optimal management of the patient and the treating physician concludes that breaking the code is in the best interest of the patient. Whenever a code is broken, the person breaking the code must record the time, date and reasons. It must also be recorded who is unblinded as a result of breaking the code, i.e. specific study personnel and/or the patient.

6. Methods and Assessments

This study will be carried out in an outpatient setting, with an option for inpatient visits if needed, and will consist of screening and enrollment visits (designated Visit 1), followed by a treatment visit for blinded hemin or placebo administration (Visit 2), and post-treatment visits: weekly for the first month, then at3 and at 6 months. Visits 1 and 2 may be combined to occur on the same day.

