The trial will be conducted in compliance with the protocol, Good Clinical Practice (GCP)¹ and applicable regulatory requirements. The single site for this study is the University of Texas Medical Branch (UTMB) in Galveston, Texas. Conducting the study at additional sites is not planned at this time.

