4.1 Number of patient and sites

Patients to be randomized: 20

Patients to be evaluated and screened: 40

Approximately 2 patients will need to be evaluated for every patient found suitable for study and randomization. Patients who do not complete the study will need to be replaced.

This study will be conducted at UTMB. Although it will not be a project of the Porphyrias Consortium, which has been funded in part by a U54 grant from the National Institutes of Health (NIH) beginning in 2009, the other sites in the Consortium are aware of this protocol and will refer patients that seem appropriate for evaluation. The Porphyrias Consortium is one of 23 NIH-funded consortia that comprise the Rare Disease Clinical Research Network (RDCRN). Funds for the Porphyrias Consortium U54 grant is provided by the National Institute for Diabetes, Digestive and Kidney Diseases (NIDDK) and the NIH Office of Rare Diseases Research. At present, the Consortium consists of 6 sites funded by the NIH grant, and 2 satellite sites that receive some support from the American Porphyria Foundation.

The American Porphyria Foundation (APF) is an active patient support group and is a supporting partner in the Porphyrias Consortium. The U54 grant supports

Porphyria Laboratory and Center Date: June 18, 2019 IND 13,929

infrastructure for clinical research on porphyrias but not the costs of major clinical trials. Funding by the FDA Office of Orphan Product Development beginning in September 2014 supports costs for this study and an acute treatment study, which is also a Porphyrias Consortium single-site study conducted at UTMB. Recordati Rare Diseases, the manufacturer of Panhematin[™], provides some additional grant support for both studies and supplies study drug at no cost.

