12.5 Interim analyses

An interim analysis is planned after completion of 10 subjects, to determine a reasonable estimate of the variance, as stated above in 12.4. Given the change in inclusion criteria, a logistic model will be fit to assess the change in recurrence rate by dose. We do not, however, expect that the dose or regimen effect will be statistically significant or have a substantial effect on the outcome.

13. Ethical considerations

The study will be conducted in accordance with accepted standards for human studies, including the Declaration of Helsinki. The study will be approved by the IRB at UTMB, as will changes made in study documents as appropriate.

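### Section 5.7 discloses a single block size of 4 at a one-site trial with a difficult blind, so assignments become partly predictable if others in the block are known or inferred (minor)

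*Combined protocol and SAP*

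**What the plan says.** Section 5.7 of the combined protocol and SAP describes a "double-blind, symmetrically randomized, parallel group trial study". Treatment "will be assigned by the study statistician, who will inform the Pharmacy of the assignment". On the method it says only: "Randomization will be in blocks of 4, and occur after the inclusion and exclusion criteria are satisfied". It mentions no second block size, no stratification and no restriction on who may know the size.

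The protocol's opening statement reads: "The single site for this study is the University of Texas Medical Branch (UTMB) in Galveston, Texas". Section 4.1 gives "Patients to be randomized: 20". The list is therefore one sequence of five blocks, each split 2:2.

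On the blind, Section 5.5 concedes: "Blinding of treatment with a darkly colored, intravenous drug poses significant challenges". Section 5.2 explains that a look-alike for the black hemin solution cannot be made, so saline is used behind an opaque container, drapes and a blindfold, with one unblinded nurse. Section 5.5 asks that infusion problems be handled without unblinding where that can be done, and that threats to the blind be recorded. Section 5.7 adds: "The randomization code for a particular subject can be broken", when the treating physician judges it to be in the patient's interest.

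**The concern.** The protocol is the working document of the staff who enrol patients and record attacks, so they can read the block size. With a known size and equal split, an allocation that becomes known or is inferred carries information about the rest of its block. That includes patients not yet enrolled and patients still in follow-up.

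The plan leaves several ways for this to happen:
- individual code breaks (5.7);
- infusion problems that compromise the blind (5.5);
- repeated infusions in some patients (3.1), although 5.5 bases feasibility on a single administration;
- ALA and PBG results, which Section 1.1 says fall sharply after hemin and which the site's own laboratory measures (6.2.2). Samples at follow-up visits are optional, so this route is possible rather than certain.

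The stake is selection and judgement. Section 3.2 calls the symptoms variable and subjective, two exclusion criteria in 4.4 rest on the investigator's judgement, and Section 11 allows exclusions from the efficacy analysis for certain deviations. With about 10 patients per arm, a few influenced decisions could matter.

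**Working it through.** **Plan's own figure.** The documents give no figure for predictability. The only design calculation is in 12.4: about 80% power with 10 per group at recurrence 0.8 v 0.2. The pooled normal approximation gives (0.6 − 1.96 × 0.2236) / 0.1789 = 0.904, a power of 81.7%, so the figure reproduces. It does not bear on this point; only the illustrative recurrence rates are used below.

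**Inputs.** Block size 4 and equal allocation (5.7); 20 patients (4.1); recurrence 0.8 v 0.2 and, as the second example, 0.8 v 0.38 (12.4). A 2:2 block has 6 equally likely arrangements.

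**One allocation known.** Of the other three patients, two are on the opposite arm. Each is therefore on the opposite arm with probability 2/3, and none is certain.

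**Two or three known.** Two known allocations match with probability 1/3, and the other two patients are then certain. If they differ (2/3), the others stay at 50:50. With three known, the fourth is always certain.

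**Worst case: every earlier allocation known.**

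| Position | Best guess correct | Certain in advance |
|---|---|---|
| 1 | 0.500 | 0 |
| 2 | 0.667 | 0 |
| 3 | 1/3 × 1 + 2/3 × 1/2 = 0.667 | 1/3 |
| 4 | 1.000 | 1 |
| Mean | 2.833 / 4 = 0.708 | 1.333 / 4 = 0.333 |

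Over 20 patients, about 6.7 assignments are certain and 14.2 are guessed correctly, against 10 by chance.

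**Outcomes only, no unblinding.** Staff guess placebo after an attack and active after none, and know where blocks start.
- At 0.8 v 0.2 each earlier arm is inferred correctly 80% of the time. Position 2: 0.8 × 2/3 + 0.2 × 1/3 = 0.60. Position 3: 0.60. Position 4: the first three hold two patients of the opposite arm, and a majority call is right with probability 0.64 + 0.32 × 0.2 = 0.704. Mean (0.50 + 0.60 + 0.60 + 0.704) / 4 = 60.1%.
- At 0.8 v 0.38 accuracy per earlier patient is (0.80 + 0.62) / 2 = 0.71. Position 2: 0.71 × 2/3 + 0.29 × 1/3 = 0.57. Enumeration gives 0.583 and 0.620 for positions 3 and 4. Mean 56.8%.

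**Varying sizes.** The guesser knows the scheme but not the size of the current block.

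| Scheme | Certain, earlier arms known | Mean guess, earlier arms known | Mean guess, outcomes only (0.8 v 0.2) |
|---|---|---|---|
| Fixed 4 | 33.3% | 70.8% | 60.1% |
| One 4 and one 6 in random order within each 10 (enumeration) | 18.7% | 69.3% | 58.2% |
| 4 or 6 drawn independently (20,000 simulated lists of 20) | 5.8% | 68.5% | not computed |

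Varying the size removes much of the certainty and little of the average predictability.

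**The case against.** The strongest reply is that the blind must fail before block size matters, and the plan works to prevent that. Only the statistician, one or two pharmacy staff and one infusion nurse know the arms. The nurse takes no other part in care or data collection, and blinded staff leave the room (5.2, 5.5). Early attack treatment is arranged so as not to disclose the arm (5.3, 5.6), and code breaks are individual and documented (5.7). If the blind did fail broadly, assessors would know each patient's arm directly, whatever the block size. This stands: the 33% and 71% are a worst case, and block size adds harm only by carrying information to other patients in the block.

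The outcome-only figures are also soft. The rates in 12.4 are examples, and that section doubts whether the earlier series is a guide. Follow-up runs for weeks, so some outcomes will be unknown when the next patient is randomised. Blocks of 4 also serve a purpose, since they hold the arms close in a very small trial.

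What the reply does not remove is that the size is printed where enrolling staff can read it, while the plan itself foresees breaches and code breaks. Custody of the list by the statistician and Pharmacy does not hide the block size.

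**Conclusion.** The point holds as a minor weakness. A single disclosed size of 4 makes assignments partly predictable: 67% for each other patient in the block after one known allocation, about 57% to 60% on average from outcomes alone under the illustrative rates, and at worst 71% with one third certain. The last two results assume that staff know where blocks begin. The worst case also assumes that all earlier allocations are known, and the outcome-only case that all earlier outcomes are.

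Two stronger inferences are tempting and should not be drawn. A reader might infer that any known allocation gives away the rest of its block. It does not: certainty needs two matching allocations or three known ones.

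A reader might also note that 4 does not divide 10 and infer a calculable chance of unequal arms at the interim, or that another block scheme would guarantee equal arms there. Section 12.5 says "An interim analysis is planned after completion of 10 subjects", Sections 3.1 and 3.2 make that number approximate, and 4.1 replaces patients who do not complete. The interim is not tied to the tenth randomisation, so neither inference is supported.

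**What to change.** In 5.7, delete the block size and write: *permuted blocks of randomly varying size, not disclosed to site staff*. Keep the sizes in a restricted randomisation file held by the statistician and Pharmacy, and issue a new list for patients not yet randomised. Sizes of 4 and 6 would serve. One of each in random order within every ten keeps exact balance at 20 randomised. Independent draws leave fewer certain assignments if the scheme leaks (5.8% against 18.7%) but may end at 11:9.

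The cost is one sentence and a new list. Treatment, visits, sample size and analysis are unchanged. The downside is that the running difference between arms can reach 3 instead of 2. Most of the benefit comes from non-disclosure, so varying the sizes while still printing them would achieve little.

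Staff who have read the current text already know the size used so far, so the change protects only patients randomised under the new list.
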